#### 5.2.2 Specify inclusion/exclusion criteria for cohort entry and define the index date

Inclusion and exclusion criteria were adapted from the trial as closely as possible. Definitions for all inclusion/exclusion are provided in **Appendix** and are summarized in the flowcharts below.

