#### 5.3 Flowchart of the study cohort assembly For Apixaban vs. Rivaroxaban

	0	ptum CDM	IBM® M	arketScan®	CMS - NOAC	
	Less Excluded Patients	Remaining Patients	Less Excluded Patients	Remaining Patients	Less Excluded Patients	Remaining Patients
All patients in our database		81,796,156		205,537,714		6,886,908
Patients with Apixaban/Rivaroxaban [measured between Dec 28, 2012 and June 30, 2020.]		856,974		685,749		2,232,416
Excluded due to insufficient enrollment [-180, 0]	-118,628 (14%)	738,346	-54,038 (8%)	631,711	-373,136 (17%)	1,859,280
After wash-out for prior use of reference (Rivaroxaban) [-180, -1]	-206,560 (28%)	531,786	-211,703 (34%)	420,008	-601,148 (32%)	1,258,132
After wash-out for prior use of exposure (Apixaban) [-180, -1]	-278,943 (52%)	252,843	-170,997 (41%)	249,011	-549,695 (44%)	708,437
Excluded because patient qualified in >1 exposure category	-13 (<1%)	252,830	-24 (<1%)	248,987	-54 (<1%)	708,383
Exclusion of Missing Age [-180, 0]	-7 (<1%)	252,823	-0 (<1%)	248,987	-151 (<1%)	708,232
Exclusion of Gender (Exclude Missing Values) [start of all available data, 0]	-17 (<1%)	252,806	-0 (<1%)	248,987		
Inclusion of Age >= 18 [0,0]	-170 (<1%)	252,636	-415 (<1%)	248,572		
Inclusion of Non-Valvular A-fib [- 180,0]	-104,252 (41%)	148,384	-132,025 (53%)	116,547	-264,650 (37%)	443,581
Exclusion of Anticoagulant Use [- 180, 0]	-7,414 (5%)	140,970	-6,140 (5%)	110,407	-34,042 (8%)	409,539
Exclusion of CKD Stage 4/5 or ESRD [-180,0]	-2,876 (2%)	138,094	-994 (<1%)	109,413	-7,617 (2%)	401,922
Exclusion of Dialysis or Renal Transplant) [-180, 0]	-158 (<1%)	137,936	-119 (<1%)	109,294	-421 (<1%)	401,501

Exclusion of Bleeding History [-180, 0]	-2,721 (2%)	135,215	-3,332 (3%)	105,962	-23,500 (6%)	378,001
Exclusion of Cancer [-180,0]	-5,556 (4%)	129,659	-3,177 (3%)	102,785	-14,538 (4%)	363,463
Exclusion of Weight > 120 kg [-180, 0]	-6,963 (5%)	122,696	-3,322 (3%)	99,463	-10,521 (3%)	352,942
Exclusion of Significant Liver Disease [-180, 0]	-1,781 (1%)	120,915	-892 (<1%)	98,571	-3,233 (<1%)	349,709
Exclusion of Use of Contraindicated Medications [-180, 0]	-693 (<1%)	120,222	-596 (<1%)	97,975	-2,762 (<1%)	346,947
Exclusion of Dual Antiplatelet Therapy [-180,0]	-3,219 (3%)	117,003	-2,642 (3%)	95,333	-9,829 (3%)	337,118
Exclusion of Other Heart Conditions [-180,0]	-3,603 (3%)	113,400	-3,056 (3%)	92,277	-7,962 (2%)	329,156
Exclusion of Other Indication of Long-Term Anticoagulation [-180, 0]	-489 (<1%)	112,911	-293 (<1%)	91,984	-1,447 (<1%)	327,709

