Heparin Sodium Porcine/Dextrose (5% in water or 5% in water/PF), Heparin Sodium, Program Sodium Porcine, and Warfarin Sodium	
2       Creatine clearance < 15 ml/min calculated with the Cockcroft-Gault formula	
Any contradiction for anticoagulation with apixaban or rivaroxaban as determined by the treating physician such as, but not limited to one of the following:	
Mesaured [-180, 0] in any diagnosis position and in an inpatient setting (transfusion codes required for non-critical sites)	
Maior Bleeding See "Major Bleeding" Sheet	
Active Bleeding     Measured [-180,0] in any diagnosis position in an inpatient setting (transfusion codes not required for non-critical sites)     Clinically Relevant Non-Major Bleeding Events	
See "CRNM Bleeds Sheet"	
Measuered [-180, 0] in any diagnosis position in an inpatient or oupatient setting:           DVT           ICD-9 Diagnosis: 451.1x, 451.2x, 451.81, 451.9x, 453.1x, 453.2x, 453.8x, 453.9x, 453.40, 453.41, 453.42, 453.0           ICD-10 Diagnosis: 180.1x, 180.2, 180.3, 180.9, 182.0, 182.1, 182.2x (except 182.21), 182.4x, 182.6x, 182.80, 182.90, 181.A1x, 182.E1x, 182.C1x	
2) Other Indication for anticoagulation (e.g. mechanical valves, venous thromosis)       PE         ICD-9 Diagnosis:       415.1, 415.10, 415.11, 415.12, 415.13, 415.5, 415.16, 417.17, 415.19, 41	
Prosthetic Heart Valve ICD-9 Diagnosis: V43.3 ICD-10 Diagnosis: Z95.2	

1

	Measured [-180, 0] in prescription claims	
3) Dual Antiplatelet Use	Use of Antiplaelets Any of the following: cilostazol, dipyridamole, ticlopidine HCl, aspirin, clopidogrel bisulfate, prasugrel HCl, ticagerlor, aspirin/dipyridamole, ezetimibe	

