- Diabetic Neuropathy; n (%)	1,924 (5.6%)	1,921 (5.6%)	0	1,054 (3.4%)	1,085 (3.5%)	-0.005479185	4,403 (3.7%)	4,477 (3.8%)	-0.005263632	7,381 (4.0%)	7,483 (4.1%)	-0.005072843
- Diabetic Nephropathy; n (%) - Diabetes with peripheral circulatory disorders; n (%)	1,713 (5.0%) 168 (0.5%)	1,643 (4.8%) 149 (0.4%)	0.00926502 0.014941191	574 (1.9%) 159 (0.5%)	549 (1.8%) 157 (0.5%)	0.007421163	2,524 (2.1%) 753 (0.6%)	2,577 (2.2%) 767 (0.6%)	-0.006894503	4,811 (2.6%) 1,080 (0.6%)	4,769 (2.6%) 1.073 (0.6%)	0
- Diabetes with peripheral circulatory disorders and lower extremity amputation; n (%)	320 (0.9%)	299 (0.9%)	0	213 (0.7%)	213 (0.7%)	0	1,121 (0.9%)	1,129 (0.9%)	0	1,654 (0.9%)	1,641 (0.9%)	0
- Diabetes with unspecified complications; n (%) - Diabetes mellitus without mention of complications; n (%)	581 (1.7%) 7,987 (23.4%)	565 (1.7%) 7,960 (23.4%)	0	431 (1.4%) 6,409 (20.7%)	442 (1.4%) 6,433 (20.8%)	0 -0.002465992	1,218 (1.0%) 28,342 (23.8%)	1,240 (1.0%) 28,423 (23.9%)	0 -0.002346503	2,230 (1.2%) 42,738 (23.2%)	2,247 (1.2%) 42,816 (23.3%)	0 -0.00236728
- Diadetes mentas windut mentan of complications, in (%) - Hypertension; n (%)	26,217 (77.0%)	26,232 (77.0%)	0	21,209 (68.6%)	21,234 (68.7%)	-0.002465992	20,342 (23.0%) 100,576 (84.4%)	100,572 (84.4%)	0	42,738 (23.2%) 148,002 (80.4%)	42,010 (23.3%) 148,038 (80.4%	
- Hyperlipidemia; n (%)	19,147 (56.2%) 766 (2.2%)	19,028 (55.9%) 779 (2.3%)	0.006044439 -0.006742995	15,159 (49.0%) 647 (2.1%)	15,017 (48.6%) 639 (2.1%)	0.008002369	61,613 (51.7%) 2.681 (2.3%)	61,604 (51.7%) 2.693 (2.3%)	0	95,919 (52.1%) 4.094 (2.2%)	95,649 (52.0%) 4.111 (2.2%)	0.002001684
-Acute Mi; n (%) - ACS/unstable angina; n (%)	766 (2.2%) 771 (2.3%)	779 (2.3%) 751 (2.2%)	-0.006742995	621 (2.0%)	595 (1.9%)	0.007232055	2,681 (2.3%) 2,555 (2.1%)	2,693 (2.3%) 2,574 (2.2%)	-0.006894503	4,094 (2.2%) 3,947 (2.1%)	4,111 (2.2%) 3,920 (2.1%)	0
- Old MI; n (%)	1,430 (4.2%)	1,379 (4.0%)	0.010086356	606 (2.0%)	633 (2.0%)	0	4,808 (4.0%)	4,745 (4.0%)	0	6,844 (3.7%)	6,757 (3.7%)	0
- Stable angina; n (%) - Coronary atherosclerosis and other forms of chronic ischemic heart disease; n (%)	1,478 (4.3%) 8.484 (24.9%)	1,501 (4.4%) 8.497 (24.9%)	-0.004902461 0	935 (3.0%) 6.205 (20.1%)	935 (3.0%) 6.178 (20.0%)	0.002497663	3,675 (3.1%) 29.809 (25.0%)	3,654 (3.1%) 29,653 (24,9%)	0.002310945	6,088 (3.3%) 44,498 (24,2%)	6,090 (3.3%) 44,328 (24.1%)	0

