Medications - ARBs; n (%) Medications - Alpha blockers; n (%)	7,534 (22.1%) 3,937 (11.6%)	7,581 (22.3%) 3,937 (11.6%)	-0.004812436	6,867 (22.2%) 2,825 (9.1%)	6,809 (22.0%) 2,855 (9.2%)	0.004820215	28,936 (24.3%) 14.595 (12.3%)	28,724 (24.1%) 14,663 (12.3%)	0.004669699	43,337 (23.5%) 21.357 (11.6%)	43,114 (23.4%) 21,455 (11,7%)	0.002360241
Medications - Beta blockers; n (%)	22,348 (65.6%)	22,416 (65.8%)	-0.004213095	20,697 (66.9%)	20.720 (67.0%)	-0.002125882	81,685 (68.6%)	81,727 (68.6%)	0	124,730 (67.7%)	124,863 (67.8%	) -0.002139345
Medications - Loop Diuretics; n (%) Medications - Other diuretics: n (%)	6,871 (20.2%) 1,520 (4,5%)	6,783 (19.9%) 1,532 (4,5%)	0.007493037	4,918 (15.9%) 1,206 (3.9%)	4,920 (15.9%) 1,219 (3,9%)	0	27,836 (23.4%) 5,513 (4.6%)	27,874 (23.4%) 5,482 (4.6%)	0	39,625 (21.5%) 8,239 (4.5%)	39,577 (21.5%) 8,233 (4.5%)	0
Medications - Use of nitrates: n (%)	1,576 (4.6%)	1,606 (4.7%)	-0.004749134	1,188 (3.8%)	1,207 (3.9%)	-0.005197523	7,347 (6.2%)	7,306 (6.1%)	0.004162423	10,111 (5.5%)	10,119 (5.5%)	ő
Medications - Use of statins; n (%) Medications - Use of other lipid-lowering drugs; n (%)	17,122 (50.3%) 1.232 (3.6%)	17,176 (50.4%) 1.231 (3.6%)	-0.00200005	14,087 (45.6%) 1.353 (4.4%)	14,047 (45.4%) 1.326 (4.3%)	0.004016307 0.004902461	63,600 (53.4%) 5.124 (4.3%)	63,607 (53.4%) 5,109 (4,3%)	0	94,809 (51.5%) 7.709 (4.2%)	94,830 (51.5%) 7.666 (4.2%)	0
Medications - calcium channel blockers; n (%)	12,788 (37.5%)	12,824 (37.6%)	-0.002065043	11,453 (37.0%)	11,469 (37.1%)	-0.002070657	46,948 (39.4%)	46,720 (39.2%)	0.004094872	71.189 (38.7%)	71,013 (38.6%)	0.002053611
er Comorbidity - Osteoporosis; n (%) er Comorbidity - Dementia; n (%)	2,752 (8.1%) 2,507 (7.4%)	2,723 (8.0%) 2,505 (7.4%)	0.003675589	1,291 (4.2%) 1,220 (3.9%)	1,266 (4.1%) 1,211 (3.9%)	0.005013965	11,020 (9.3%) 8,916 (7.5%)	10,950 (9.2%) 8,905 (7.5%)	0.003451489	15,063 (8.2%) 12,643 (6.9%)	14,939 (8.1%) 12.621 (6.9%)	0.003654958
er Comorbidity - Hyperthyroidism + Hypothyroidism + Other disorders of thyroid gland ; n (%)	7,094 (20.8%)	7,038 (20.7%)	0.002465992	4,914 (15.9%)	4,969 (16.1%)	-0.005455468	14,854 (12.5%)	14,982 (12.6%)	-0.003018552	26,862 (14.6%)	26,989 (14.7%)	-0.002828003

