DM Medications - 1st and 2nd Generation SUs ; n (%) DM Medications - DPP-4 Inhibitors; n (%)	2,118 (6.2%) 860 (2.5%)	2,081 (6.1%) 888 (2.6%)	0.004162423 -0.006343679	1,622 (5.2%) 978 (3.2%)	1,634 (5.3%) 979 (3.2%)	-0.004483651	7,542 (6.3%) 3,422 (2.9%)	7,589 (6.4%) 3,455 (2.9%)	-0.00410072	11,282 (6.1%) 5,260 (2.9%)	11,304 (6.1%) 5,322 (2.9%)	0
DM Medications - GLP-1 RA; n (%)	345 (1.0%)	349 (1.0%)	0	452 (1.5%)	454 (1.5%)	0	793 (0.7%)	774 (0.6%)	0.012444223	1,590 (0.9%)	1,577 (0.9%)	0
DM Medications - SGLT-2 Inhibitors ; n (%)	317 (0.9%)	317 (0.9%)	0	387 (1.3%)	384 (1.2%)	0.009000794	524 (0.4%)	519 (0.4%)	0	1,228 (0.7%)	1,220 (0.7%)	0
DM Medications - Metformin; n (%) Other Medications - Use of NSAIDs: n (%)	4,637 (13.6%) 4,170 (12.2%)	4,625 (13.6%) 4,141 (12.2%)	0	3,972 (12.8%) 4 177 (13.5%)	3,996 (12.9%) 4,205 (13.6%)	-0.002988238 -0.002921785	15,017 (12.6%) 15.933 (13.4%)	15,014 (12.6%) 15.888 (13.3%)	0 002940191	23,626 (12.8%) 24,280 (13.2%)	23,635 (12.8%) 24,234 (13.2%)	0
Other Medications - Use of other hypertension drugs; n (%)	2,254 (6.6%)	2,221 (6.5%)	0.004041947	1,668 (5.4%)	1,691 (5.5%)	-0.004405265	8,885 (7.5%)	8,941 (7.5%)	0	12,807 (7.0%)	12,853 (7.0%)	ō
Other Medications - Digoxin; n (%)	2,219 (6.5%)	2,219 (6.5%)	0	2,082 (6.7%)	2,078 (6.7%)	0	10,307 (8.7%)	10,355 (8.7%)	0	14,608 (7.9%)	14,652 (8.0%)	-0.003696624
Other Medications - Use of Anti-arrhythmics; n (%) Other Medications - Use of antipsychotics: n (%)	5,454 (16.0%) 632 (1.9%)	5,437 (16.0%) 603 (1.8%)	0 007421163	6,102 (19.7%) 409 (1.3%)	6,071 (19.6%) 407 (1.3%)	0.002516669	21,156 (17.8%) 3.028 (2.5%)	21,105 (17.7%) 3.074 (2.6%)	0.002617178	32,712 (17.8%) 4.069 (2.2%)	32,613 (17.7%) 4 084 (2.2%)	0.002617178
Other Medications - Use of dementia meds; n (%)	1,093 (3.2%)	1,091 (3.2%)	0	625 (2.0%)	634 (2.1%)	-0.007057056	5,249 (4.4%)	5,267 (4.4%)	0	6,967 (3.8%)	6,992 (3.8%)	0
Other Medications - Use of antiparkinsonian meds; n (%)	857 (2.5%)	861 (2.5%)	0	625 (2.0%)	631 (2.0%)	0	3,737 (3.1%)	3,654 (3.1%)	0	5,219 (2.8%)	5,146 (2.8%)	0
Other Medications - Use of anxiolytics/hypnotics; n (%) Other Medications - Use of anticonvulsants; n (%)	1,623 (4.8%) 3,791 (11.1%)	1,628 (4.8%) 3,820 (11.2%)	0 -0.003177126	1,745 (5.6%) 2,559 (8.3%)	1,763 (5.7%) 2,524 (8.2%)	-0.004331176 0.003634718	7,389 (6.2%) 13,875 (11.6%)	7,356 (6.2%) 13,931 (11.7%)	0 -0.003116982	10,757 (5.8%) 20,225 (11.0%)	10,747 (5.8%) 20,275 (11.0%)	0

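### Exclusion 3 is named for dual antiplatelet use, but its stated claims definition removes anyone with a single listed agent, ezetimibe included

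*Combined protocol and SAP*

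**What the plan says.** Appendix A pairs each trial criterion with a claims definition. Item 3 of the contraindication list is "3) Dual Antiplatelet Use". Its claims definition, measured in prescription claims over [-180, 0], is "Any of the following: cilostazol, dipyridamole, ticlopidine HCl, aspirin, clopidogrel bisulfate, prasugrel HCl, ticagerlor, aspirin/dipyridamole, ezetimibe".

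The flowchart in section 5.3 labels the matching step "Exclusion of Dual Antiplatelet Therapy [-180,0". Section 5.2.2 states that "Inclusion and exclusion criteria were adapted from the trial as closely as possible" and adds that the Appendix holds the definitions, which the flowcharts summarise. The cohort summary in section 5.1 does not mention antiplatelets.

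Appendix B lists "Medications - Use of other lipid-lowering drugs; n" among the covariates balanced by matching, so lipid-lowering treatment is otherwise adjusted for and is not a ground for exclusion.

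**The concern.** A programmer working from the Appendix would exclude on one dispensing of one agent. A reader of the flowchart would assume that two agents were needed. These are different cohorts, and the study's primary outcome is bleeding, for which antiplatelet use is a natural baseline risk factor.

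The ezetimibe entry is a separate problem. Its presence in an antiplatelet list removes patients for a reason the criterion does not contain, while the rest of the plan adjusts for lipid-lowering drugs.

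What is at stake is mainly eligibility and reporting: the cohort is narrower than its label says, in a study meant to follow a trial's criteria closely. A second question arises only if the executed query did not follow the written definition. Single-agent users would then be in the cohort, and one would want them covered by the propensity score.

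**Working it through.** **Label against definition.** The label requires dual use. The definition is satisfied by any one listed agent, with no count of agents, no overlap and no days' supply. Section 5.2.2 settles which of the two is the stated rule: the Appendix definition, with the flowchart row as its short name.

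**The flowchart row (section 5.3).** Remaining = entering − removed; share = removed / entering.

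| Database | Entering | Removed | Remaining | Share |
|---|---|---|---|---|
| Optum CDM | 120,222 | 3,219 | 117,003 | 2.7% |
| MarketScan | 97,975 | 2,642 | 95,333 | 2.7% |
| CMS | 346,947 | 9,829 | 337,118 | 2.8% |
| Sum | 565,144 | 15,690 | 549,454 | 2.8% |

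All three printed remainders reproduce, and each share rounds to the printed 3%.

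**Upper bound on patients affected.** The final cohorts sum to 111,950 + 91,660 + 325,926 = 529,536. If every removed patient were wrongly removed and none fell to a later step, the number would be 15,690 / 529,536 = 3.0% of the final cohort. True dual users are among the 15,690, so the real figure is lower. The documents do not allow it to be narrowed further.

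**Ezetimibe.** In the unmatched pooled columns of Appendix B, other lipid-lowering drugs are recorded in 10,050 + 12,049 = 22,099 of 230,439 + 298,310 = 528,749 patients (4.2%). The drugs in that category are not listed, so this does not show whether ezetimibe users were removed.

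**Power.** Section 10 gives 1,354.77 events for Optum and power 0.98409 at HR 0.8. With 1:1 allocation and two-sided alpha 0.05, power = Φ(√(events/4) × |ln HR| − 1.96) = Φ(18.404 × 0.2231 − 1.96) = Φ(2.147) = 0.984, which agrees. Suppose all 3,219 Optum patients returned and the matched number grew in proportion. Events would be 68,134 × (111,950 + 3,219) / 111,950 × 19.8839 / 1,000 = 1,393.7, and power 0.986. The same step for MarketScan moves 0.9964 to 0.9970.

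**Covariates.** The readable drug rows of Appendix B include "Other Medications - Use of NSAIDs: n" but none named for antiplatelets, aspirin or clopidogrel. In the matched table the cardiovascular drugs run from ACE inhibitors to calcium channel blockers and straight on to osteoporosis with no visible gap. Other rows of these tables were lost in reading, so the absence is suggestive only. Related conditions are balanced after matching, with 184,107 per arm:

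- "Coronary atherosclerosis and other forms of chronic ischemic heart disease; n": 44,498 (24.2%) on rivaroxaban against 44,328 (24.1%) on apixaban.
- Ischemic stroke: 19,322 (10.5%) against 19,233 (10.4%).

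**The case against.** The strongest reply is that a trial label above a broader claims proxy is the normal form of Appendix A. More than 72 hours of anticoagulation becomes any anticoagulant claim in 180 days. Liver disease with coagulopathy becomes two separate exclusions. Weight above 120 kg includes bypass-surgery codes. The claims cell for item 3 carries its own heading for antiplatelet use without the word dual. The Appendix legend has a category for stand-in definitions, and the marking of each row did not survive the PDF reading. The trial criterion itself sits in an open physician list ("such as, but not limited to one of the following"), so the trial may also exclude some single-agent users. Finally, prescription claims miss over-the-counter aspirin. A rule requiring two claimed agents would keep a patient who takes one claimed agent plus purchased aspirin, whereas the written rule excludes that patient.

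Much of this stands. A one-agent proxy may be deliberate and defensible, and a two-agent overlap rule is not clearly the better emulation. What does not fall away is that nothing readable at item 3 says it is a proxy, both labels still say dual, and no proxy argument explains ezetimibe. The list comes from a broken table, however, so a truncated last entry cannot be ruled out.

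A reader might go further and infer that a dual rule was actually run, because only 2.8% were removed while coronary disease remains in 23.8% and 26.4% of the unmatched pooled arms. The documents do not support that step. Uncaptured aspirin could also explain a low count, and section 5.2.2 points to the Appendix rule.

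**Conclusion.** The label and the stated definition of exclusion 3 disagree, and the agent list includes a drug that the plan's own approach would treat as a lipid-lowering covariate. As written, single-agent and ezetimibe-only users are removed under a criterion naming dual use. The row accounts for 15,690 patients (2.8% of those entering it). The part due to the mismatch is unknown and at most 3.0% of the final cohort.

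A reader might infer that antiplatelet use is an unadjusted confounder in the comparison. That is not shown. Under the written rule, patients with a claim for a listed agent are out at baseline in both arms. The concern arises only if the executed query departed from that rule, and it rests on an absence in damaged tables. Related vascular conditions are balanced, power is unaffected, and no hazard-ratio bias is demonstrated.

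The conclusion assumes that the printed agent list is complete and that the Appendix definition was the one intended. It merits correction before the analysis; it does not threaten the design.

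**What to change.** Section 13 shows no report name or date for the comparative analysis, so the following can be done before it is run.

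1. Check the executed query and state in Appendix A which rule produced the flowchart row.
2. Remove ezetimibe from the antiplatelet list, unless the printed entry proves to be a truncation or reading artefact. In that case, print the full entry.
3. Reconcile label and definition in one of two ways. Either state that any claimed antiplatelet is a deliberate proxy, note that over-the-counter aspirin is not captured, and relabel both the Appendix A item and the flowchart row. Or code the dual criterion, stating the number of agents and the overlap required.
4. If the executed rule leaves single-antiplatelet users in the cohort, add baseline antiplatelet use to the propensity score and to the Appendix B balance table.

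The cost is a query check and a wording change. One re-run of the cohort, the match and the power tables is needed only if the rule, the agent list or the covariate list changes. No new data are required.

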Appendix A
------------

Г	Measured [-180, 0] in any diagnosis position and inpatient and outpatient care setting	1
	ICD-9 Diagnosis:         394.0           ICD-10 Diagnosis:         105.0	
	Mitral Rheumatic Insufficiency ICD-9 Diagnosis: 394.1 ICD-10 Diagnosis: 105.1	
12	Mitral Stenosis with Insufficiency ICD-9 Diagnosis: 394.2 ICD-10 Diagnosis: 105.2	
	Other and Unspecified Mitral Valve Disorders ICD-9 Diagnosis: 394.9 ICD-10 Diagnosis: 105.9, 105.8	
9	Prosthetic Heart Valve ICD-9 Diagnosis: V43.3 ICD-10 Diagnosis: 295.2 ICD-10 Diagnosis: 295.2	

# Information from Trial Trial Name: COBRRA - AF https://clinicaltrials.gov/ct2/show/NCT04642430 NCT: NCT04642430 Therapeutic Area: Cardiology RCT Category: Equivalence/Superiority Brand Name: Eliquis and Xarelto Generic Name: Apixaban and Rivaroxaban Sponsor: Ottwa Hospital Research Institute Year: 2020 - Present Measurable Endpoint: Major Bleeding and Clinically Relevant Non-Major Bleeding Exposure: Apixaban Comparator: Rivaroxaban Populuation: Men and women ages 18 and older presenting with AF No. of Patients: 3,018 Power: TBD

#### ICI

I Т

ICD-9 Dx	
336.1	VASCULAR MYELOPATHIES
363.61	CHOROIDAL HEMORRHAGE UNSPECIFIED
363.62	EXPULSIVE CHOROIDAL HEMORRHAGE
376.32	ORBITAL HEMORRHAGE
377.42	HEMORRHAGE IN OPTIC NERVE SHEATHS
379.23	VITREOUS HEMORRHAGE
431	INTRACEREBRAL HEMORRHAGE
432	OTHER AND UNSPECIFIED INTRACRANIAL HEMORRHAGE
432	NONTRAUMATIC EXTRADURAL HEMORRHAGE
432.1	SUBDURAL HEMORRHAGE
432.9	UNSPECIFIED INTRACRANIAL HEMORRHAGE
	HEMARTHROSIS
	HERARTHROSIS INVOLVING SHOULDER REGION
	HEMARTHORSIS INVOLVING UPPER ARM
	HEMARTHROSIS INVOLVING HAND
	HEMARTHROSIS INVOLVING PELVIC REGION AND THIGH
-	HEMARTHROSIS INVOLVING ANKLE AND FOOT
	HEMARTHROSIS INVOLVING MULTIPLE SITES
	NONTRAUMATIC HEMATOMA OF SOFT TISSUE
	SUBARACHNOID SUBDURAL AND EXTRADURAL HEMORRHAGE FOLLOWING INJURY
	SUBARACHNOID HEMORRHAGE FOLLOWING INJURY WITHOUT OPEN INTRACRANIAL WOUND WITH STATE OF CONSCIOUSNESS UNSPECIFIED
	SUBARACHNOID HEMORRHAGE FOLLOWING INJURY WITHOUT OPEN INTRACRANIAL WOUND WITH NO LOSS OF CONSCIOUSNESS
	SUBARACHNOID HEMORRHAGE FOLLOWING INJURY WITHOUT OPEN INTRACRANIAL WOUND WITH MODERATE (1 - 24 HOURS) LOSS OF CONSCIOUSNESS)
	SUBARACHNOID HEMORRHAGE FOLLOWING INJURY WITHOUT OPEN INTRACRANIAL WOUND WITH PROLONGED (MORE THAN 24 HOURS) LOSS OF CONSCIOUSNESS WITHOUT RETURN TO PRE-EXISTING CONSCIOUS LEVEL
	SUBARACHNOID HEMORRHAGE FOLLOWING INJURY WITHOUT OPEN INTRACRANIAL WOUND WITH LOSS OF CONSCIOUSNESS OF UNSPECIFIED DURATION
	SUBARACHNOID HEMORRHAGE FOLLOWING INJURY WITHOUT OPEN INTRACRANIAL WOUND WITH CONCUSSION UNSPECIFIED SUBARACHNOID HEMORRHAGE FOLLOWING INJURY WITH OPEN INTRACRANIAL WOUND WITH STATE OF CONSCIOUSNESS UNSPECIFIED
	SUBARACHINOID HEMORRHAGE FOLLOWING INJURY WITH OPEN INTRACRANIAL WOUND WITH NO LOSS OF CONSCIOUSNESS SUBARACHNOID HEMORRHAGE FOLLOWING INJURY WITH OPEN INTRACRANIAL WOUND WITH BRIEF (LESS THAN ONE HOUR) LOSS OF CONSCIOUSNESS
	SUBARACINOID HEMORITIABLE FOLLOWING INJURY WITH OPEN INTRACRANIAL WOOND WITH BRIEF (LESS THAT ORE HOOR) LOSS OF CONSCIOUSNESS
	SUBARACHNOID HEMORRHAGE FOLLOWING INJURY WITH OPEN INTRACRANIAL WOUND WITH CONCUSSION UNSPECIFIED
	SUBDURAL HEMORRHAGE FOLLOWING INJURY WITHOUT OPEN INTRACRANIAL WOUND WITH STATE OF CONSCIOUSNESS UNSPECIFIED
	SUBDURAL HEMORRHAGE FOLLOWING INJURY WITHOUT OPEN INTRACRANIAL WOUND WITH BRIEF (LESS THAN ONE HOUR) LOSS OF CONSCIOUSNESS
	SUBDURAL HEMORRHAGE FOLLOWING INJURY WITHOUT OPEN INTRACRANIAL WOUND WITH PROLONGED (MORE THAN 24 HOURS) LOSS OF CONSCIOUSNESS WITHOUT RETURN TO PRE-EXISTING CONSCIOUS LEVEL
	SUBDURAL HEMORRHAGE FOLLOWING INJURY WITH OPEN INTRACRANIAL WOUND
852.3	SUBDURAL HEMORRHAGE FOLLOWING INJURY WITH OPEN INTRACRANIAL WOUND WITH STATE OF CONSCIOUSNESS UNSPECIFIED
852.31	SUBDURAL HEMORRHAGE FOLLOWING INJURY WITH OPEN INTRACRANIAL WOUND WITH NO LOSS OF CONSCIOUSNESS
852.32	SUBDURAL HEMORRHAGE FOLLOWING INJURY WITH OPEN INTRACRANIAL WOUND WITH BRIEF (LESS THAN ONE HOUR) LOSS OF CONSCIOUSNESS
852.33	SUBDURAL HEMORRHAGE FOLLOWING INJURY WITH OPEN INTRACRANIAL WOUND WITH MODERATE (1-24 HOURS) LOSS OF CONSCIOUSNESS
	SUBDURAL HEMORRHAGE FOLLOWING INJURY WITH OPEN INTRACRANIAL WOUND WITH PROLONGED (MORE THAN 24 HOURS) LOSS OF CONSCIOUSNESS AND RETURN TO PRE-EXISTING CONSCIOUS LEVEL
	SUBDURAL HEMORRHAGE FOLLOWING INJURY WITH OPEN INTRACRANIAL WOUND WITH PROLONGED (MORE THAN 24 HOURS) LOSS OF CONSCIOUSNESS WITHOUT RETURN TO PRE-EXISTING CONSCIOUS LEVEL
	EXTRADURAL HEMORRHAGE FOLLOWING INJURY WITHOUT OPEN INTRACRANIAL WOUND WITH BRIEF (LESS THAN 1 HOUR) LOSS OF CONSCIOUSNESS
	EXTRADURAL HEMORRHAGE FOLLOWING INJURY WITHOUT OPEN INTRACRANIAL WOUND WITH MODERATE
	EXTRADURAL HEMORRHAGE FOLLOWING INJURY WITHOUT OPEN INTRACRANIAL WOUND WITH PROLONGED (MORE THAN 24 HOURS) LOSS OF CONSCIOUSNESS WITHOUT RETURN TO PRE-24 HOURS) LOSS OF CONSCIOUSNESS-EXISTING CONSCIOUS LEVEL
	EXTRADURAL HEMORRHAGE FOLLOWING INJURY WITHOUT OPEN INTRACRANIAL WOUND WITH CONCUSSION UNSPECIFIED
	EXTRADURAL HEMORRHAGE FOLLOWING INJURY WITH OPEN INTRACRANIAL WOUND WITH PROLONGED (MORE THAN 24 HOURS) LOSS OF CONSCIOUSNESS AND RETURN TO PRE-EXISTING CONSCIOUS LEVEL
	OTHER AND UNSPECIFIED INTRACRANIAL HEMORRHAGE FOLLOWING INJURY
	OTHER AND UNSPECIFIED INTRACRANIAL HEMORRHAGE FOLLOWING INJURY WITHOUT OPEN INTRACRANIAL WOUND WITH STATE OF CONSCIOUSNESS UNSPECIFIED
	OTHER AND UNSPECIFIED INTRACRANIAL HEMORRHAGE FOLLOWING INJURY WITHOUT OPEN INTRACRANIAL WOUND WITH NO LOSS OF CONSCIOUSNESS
	OTHER AND UNSPECIFIED INTRACRANIAL HEMORRHAGE FOLLOWING INJURY WITHOUT OPEN INTRACRANIAL WOUND WITH MODERATE (1-24 HOURS) LOSS OF CONSCIOUSNESS OTHER AND UNSPECIFIED INTRACRANIAL HEMORRHAGE FOLLOWING INJURY WITHOUT OPEN INTRACRANIAL WOUND WITH PROLONGED (MORE THAN 24 HOURS) LOSS OF CONSCIOUSNESS AND RETURN TO PRE-EXISTING CONSCIOUS LEVEL
	OTHER AND UNSPECIFIED INTRACRANIAL HEMORRHAGE FOLLOWING INJURY WITHOUT OPEN INTRACRANIAL WOUND WITH PROLONGED (MORE THAN 24 HOURS) LOSS OF CONSCIOUSNESS AND RETORN TO PRE-EXISTING CONSCIOUS LEVEL
	OTHER AND UNSPECIFIED INTRACRANIAL HEMORNIAGE OLEOWING INJURY WITH OPEN INTRACRANIAL WOORD WITH NO LOSS OF CONSCIOUSNESS
	OTHER AND UNSPECIFIED INTRACRAMAL HEMORRHAGE FOLLOWING INJURY WITH OPEN INTRACRAMIAL WOUND WITH MODERATE (1-24 HOURS) LOSS OF CONSCIOUSNESS
	THER AND UNSPECTED INTRACRAMIAL HEMORPHASE FOLLOWING IN JURY WITH OPEN INTRACRAMIAL WOUND WITH OPEN UNDER THAN 24 HOURS LOSS OF CONSCIOUSNESS AND RETURN TO DREEVISTING CONSCIOUS LEVEL

853.14 OTHER AND UNSPECIFIED INTRACRANIAL HEMORRHAGE FOLLOWING INJURY WITH OPEN INTRACRANIAL WOUND WITH PROLONGED( MORE THAN 24 HOURS) LOSS OF CONSCIOUSNESS AND RETURN TO PRE-EXISTING CONSCIOUS LEVEL

853.15 OTHER AND UNSPECIFIED INTRACRANIAL HEMORRHAGE FOLLOWING INJURY WITH OPEN INTRACRANIAL WOUND WITH PROLONGED (MORE THAN 24 HOURS) LOSS OF CONSCIOUSNESS WITHOUT RETURN TO PRE-EXISTING CONSCIOUS LEVEL

866.02 LACERATION OF KIDNEY WITHOUT OPEN WOUND INTO CAVITY

363.72 HEMORRHAGIC CHOROIDAL DETACH 423 HEMOPERICARDIUM 430 SUBARACHNOID HEMORRHAGE 568.81 HEMOPERITONEUM (NONTRAUMATIC) 719.1 HEMARTHROSIS SITE UNSPECIFIED 719.13 HEMARTHROSIS INVOLVING FOREARM 719.16 HEMARTHROSIS INVOLVING LOWER LEG 719.18 HEMARTHROSIS INVOLVING OTHER SPECIFIED SITES 852 SUBARACHNOID HEMORRHAGE FOLLOWING INJURY WITHOUT MENTION OF OPEN INTRACRANIAL WOUND 852.02 SUBARACHNOID HEMORRHAGE FOLLOWING INJURY WITHOUT OPEN INTRACRANIAL WOUND WITH BRIEF (LESS THAN ONE HOUR) LOSS OF CONSCIOUSNESS 852.04 SUBARACHNOID HEMORRHAGE FOLLOWING INJURY WITHOUT OPEN INTRACRANIAL WOUND WITH PROLONGED (MORE THAN 24 HOURS) LOSS OF CONSCIOUSNESS AND RETURN TO PRE-EXISTING CONSCIOUS LEVEL 852.1 SUBARACHNOID HEMORRHAGE FOLLOWING INJURY WITH OPEN INTRACRANIAL WOUND 852.13 SUBARACHNOID HEMORRHAGE FOLLOWING INJURY WITH OPEN INTRACRANIAL WOUND WITH MODERATE (1-24 HOURS) LOSS OF CONSCIOUSNESS 852.14 SUBARACHNOID HEMORRHAGE FOLLOWING INJURY WITH OPEN INTRACRANIAL WOUND WITH PROLONGED (MORE THAN 24 HOURS) LOSS OF CONSCIOUSNESS AND RETURN TO PRE-EXISTING CONSCIOUS LEVEL 852.16 SUBARACHNOID HEMORRHAGE FOLLOWING INJURY WITH OPEN INTRACRANIAL WOUND WITH LOSS OF CONSCIOUSNESS OF UNSPECIFIED DURATION 852.2 SUBDURAL HEMORRHAGE FOLLOWING INJURY WITHOUT MENTION OF OPEN INTRACRANIAL WOUND 852.21 SUBDURAL HEMORRHAGE FOLLOWING INJURY WITHOUT OPEN INTRACRANIAL WOUND WITH NO LOSS OF CONSCIOUSNESS 852.23 SUBDURAL HEMORRHAGE FOLLOWING INJURY WITHOUT OPEN INTRACRANIAL WOUND WITH MODERATE (1-24 HOURS) LOSS OF CONSCIOUSNESS 852.24 SUBDURAL HEMORRHAGE FOLLOWING INJURY WITHOUT OPEN INTRACRANIAL WOUND WITH PROLONGED (MORE THAN 24 HOURS) LOSS OF CONSCIOUSNESS AND RETURN TO PRE-EXISTING CONSCIOUS LEVEL 852.26 SUBDURAL HEMORRHAGE FOLLOWING INJURY WITHOUT OPEN INTRACRANIAL WOUND WITH LOSS OF CONSCIOUSNESS OF UNSPECIFIED DURATION 852.29 SUBDURAL HEMORRHAGE FOLLOWING INJURY WITHOUT OPEN INTRACRANIAL WOUND WITH CONCUSSION UNSPECIFIED 852.36 SUBDURAL HEMORRHAGE FOLLOWING INJURY WITH OPEN INTRACRANIAL WOUND WITH LOSS OF CONSCIOUSNESS OF UNSPECIFIED DURATION 852.39 SUBDURAL HEMORRHAGE FOLLOWING INJURY WITH OPEN INTRACRANIAL WOUND WITH CONCUSSION UNSPECIFIED 852.4 EXTRADURAL HEMORRHAGE FOLLOWING INJURY WITHOUT MENTION OF OPEN INTRACRANIAL WOUND 852 4 EXTRADURAL HEMORRHAGE FOLLOWING INJURY WITHOUT OPEN INTRACRANIAL WOUND WITH STATE OF CONSCIOUSNESS UNSPECIFIED 852.41 EXTRADURAL HEMORRHAGE FOLLOWING INJURY WITHOUT OPEN INTRACRANIAL WOUND WITH NO LOSS OF CONSCIOUSNESS 852.44 EXTRADURAL HEMORRHAGE FOLLOWING INJURY WITHOUT OPEN INTRACRANIAL WOUND WITH PROLONGED (MORE THAN 24 HOURS) LOSS OF CONSCIOUSNESS AND RETURN TO PRE-EXISTING CONSCIOUS LEVEL EXTRADURAL HEMORRHAGE FOLLOWING INJURY WITHOUT OPEN INTRACRANIAL WOUND WITH LOSS OF CONSCIOUSNESS OF UNSPECIFIED DURATION 852.46 EXTRADURAL HEMORRHAGE FOLLOWING INJURY WITH OPEN INTRACRANIAL WOUND 852.5 852.5 EXTRADURAL HEMORRHAGE FOLLOWING INJURY WITH OPEN INTRACRANIAL WOUND WITH STATE OF CONSCIOUSNESS UNSPECIFIED 852.51 EXTRADURAL HEMORRHAGE FOLLOWING INJURY WITH OPEN INTRACRANIAL WOUND WITH NO LOSS OF CONSCIOUSNESS 852.52 EXTRADURAL HEMORRHAGE FOLLOWING INJURY WITH OPEN INTRACRANIAL WOUND WITH BRIEF (LESS THAN ONE HOUR) LOSS OF CONSCIOUSNESS EXTRADURAL HEMORRHAGE FOLLOWING INJURY WITH OPEN INTRACRANIAL WOUND WITH MODERATE (1-24 HOURS) LOSS OF CONSCIOUSNESS 852 53 852.55 EXTRADURAL HEMORRHAGE FOLLOWING INJURY WITH OPEN INTRACRANIAL WOUND WITH PROLONGED (MORE THAN 24 HOURS) LOSS OF CONSCIOUSNESS WITHOUT RETURN TO PRE-EXISTING CONSCIOUS LEVEL EXTRADURAL HEMORRHAGE FOLLOWING INJURY WITH OPEN INTRACRANIAL WOUND WITH LOSS OF CONSCIOUSNESS OF UNSPECIFIED DURATION 852.56 852.59 EXTRADURAL HEMORRHAGE FOLLOWING INJURY WITH OPEN INTRACRANIAL WOUND WITH CONCUSSION UNSPECIFIED 853 OTHER AND UNSPECIFIED INTRACRANIAL HEMORRHAGE FOLLOWING INJURY WITHOUT MENTION OF OPEN INTRACRANIAL WOUND OTHER AND UNSPECIFIED INTRACRANIAL HEMORRHAGE FOLLOWING INJURY WITHOUT OPEN INTRACRANIAL WOUND WITH BRIEF (LESS THAN ONE HOUR) LOSS OF CONSCIOUSNESS 853 02 853.06 OTHER AND UNSPECIFIED INTRACRANIAL HEMORRHAGE FOLLOWING INJURY WITHOUT OPEN INTRACRANIAL WOUND WITH LOSS OF CONSCIOUSNESS OF UNSPECIFIED 853.09 OTHER AND UNSPECIFIED INTRACRANIAL HEMORRHAGE FOLLOWING INJURY WITHOUT OPEN INTRACRANIAL WOUND WITH CONCUSSION UNSPECIFIED 853 1 OTHER AND UNSPECIFIED INTRACRANIAL HEMORRHAGE FOLLOWING INJURY WITH OPEN INTRACRANIAL WOUND WITH STATE OF CONSCIOUSNESS UNSPECIFIED 853.16 OTHER AND UNSPECIFIED INTRACRANIAL HEMORRHAGE FOLLOWING INJURY WITH OPEN INTRACRANIAL WOUND WITH LOSS OF CONSCIOUSNESS OF UNSPECIFIED DURATION 853.19 OTHER AND UNSPECIFIED INTRACRANIAL HEMORRHAGE FOLLOWING INJURY WITH OPEN INTRACRANIAL WOUND WITH CONCUSSION UNSPECIFIED 866.01 HEMATOMA OF KIDNEY WITHOUT RUPTURE OF CAPSULE WITHOUT OPEN WOUND INTO CAVITY HEMATOMA OF KIDNEY WITHOUT RUPTURE OF CAPSULE WITH OPEN WOUND INTO CAVITY 866 11 LACERATION OF KIDNEY WITH OPEN WOUND INTO CAVIT 866 12 The occurrence of Inpatient Confinement with the following attributes: Procedure Code (Any Confinement Position) is any of: { "99.05", "99.03", "99.04", "99.06" 99 05 TRANSFUSION OF PLATELETS 99.03 OTHER TRANSFUSION OF WHOLE BLOOD 99.04 TRANSFUSION OF PACKED CELLS
